9.4.4 Safety Analyses

As described in Section 9.4.2.

9.4.5 Baseline Descriptive Statistics

Baseline demographics, ophthalmic, neurodevelopmental and auditory data will be summarized using descriptive statistics or qualitatively as applicable.

9.4.6 Planned Interim Analyses

No interim analysis is planned for this pilot study. However, the Principal Investigator and designated study team members will be continually monitoring the feasibility and safety of the use of the OrCam and may terminate this study at any time for safety or administrative reasons.

9.4.7 Sub-Group Analyses

Analyses of the sub-groups will be as described in Sections 9.4.2 and 9.4.3.

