1 PROTOCOL SUMMARY

1.1 SYNOPSIS

Title:	Pilot Study of an Optic-to-Audio Device in a Pediatric Cohort with CLN3-related conditions or Low Vision
Study Description:	This is a pilot study of an augmentative visual device, OrCam MyEye 2 (OrCam), in pediatric individuals with CLN3-related conditions or low vision. We hypothesize that, given the relatively simple design and operating procedure of the device, the use of the OrCam by study participants will be safe and feasible. We also hypothesize that the device will enhance their ability to obtain visually based information.
Objectives:	
Primary Assess the safety and feasibility of OrCam use by children with CLN3 or low vision.
 
Secondary Assess the effectiveness of OrCam use by children with CLN3 or low vision.
 
Exploratory Assess the feasibility and effectiveness of OrCam use in CLN3 versus non-CLN3 groups. Optimize methods for assessing efficacy of visual accommodation/assistive devices for the CLN3/NCL population

Endpoints:	
Primary 1) Adverse events during the use of OrCam. 2) Feasibility test. 3) Feasibility questionnaire. 4) Device use diary. The assessment periods will be 1 week at study site and 1 month at home.
 
Secondary 1) Function test of using OrCam. 2) Ability questionnaire.
 
Exploratory 1) Function test. 2) Feasibility, Ability, Applicability questionnaires.

Study Population:	30 individuals age 6-18 years with low vision (20 with CLN3-related conditions, 10 without CLN3) of any gender, demographic, geographic location who meet study eligibility criteria.
Phase:	Not applicable
Description of Sites/Facilities	The NIH Clinical Center will be the only site enrolling participants.
Enrolling Participants:	
Description of Study Intervention:	The study uses the OrCam MyEye 2, a 22.5-g portable, eyeglass-mounted device that converts camera-captured inputs to auditory outputs. Its advertised functions include text reading, facial recognition, and product identification. The study participants and

Abbreviated Title: Pediatric Optic-to-Audio Device Study

[figure not shown]
Version Date: October 25, 2022

parents/guardians will be trained on how to use the device. Evaluations for primary and secondary endpoints will be done following 1 week and 1 month of device use.

Study Duration: 24-36 months.

Participant Duration: 1-2 months

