1) To compare the feasibility and efficacy of using the device between the CLN3 and non-CLN3 groups. 2) To optimize methods for assessing efficacy of visual accommodation/assistive devices for the CLN3/NCL population 3) To characterize parental objectives relating to vision-based functions for a child with CLN3 4) To assess unanticipated adaptive functions of using the OrCam. 5) To discover biochemical markers relevant to disease	1) Function test – Feasibility Scores, Feasibility, Ability, Applicability questionnaires 2) Function test – Feasibility Scores, Neuropsychologic evaluation (1-month), Feasibility, Ability, Applicability questionnaires 3) Ability, Applicability, Quality of Life questionnaires 4) Device use diary 5) Samples collection to complement Natural History	1) Individuals with CLN3 also have neurocognitive disability, whereas the non-CLN3 may not. These evaluations would provide perspectives on differences in the two groups. 2) Participants' and caregivers' perspective will be important towards informing future development of studies and interventions for visual function in the CLN3 cohort. 3) Collection of biospecimens will allow increase in numbers and statistical power for the biomarker discovery

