5.3.2 Participation of children and cognitively impaired children

CLN3 is a disease with typical onset in childhood. For age- and visual severity level-appropriate comparisons, individuals with low vision but not CLN3 will also be children. The procedures included in the protocol are reasonably commensurate with those that children with CLN3 or low vision would encounter in their expected medical care. Participants may benefit directly from the use of the OrCam. We will follow procedures outlined in **Section 10.1 Informed Consent Process** for consenting children.

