9.4.2 Analysis of the Primary Endpoints

Adverse events and Device use diary data will be provided using descriptive statistics.

Feasibility Test

Data analysis. Participants' scores will be the sum of items 1 to 5 and will range from 0 to 5. Analysis will consist of summary descriptive statistics (mean, standard deviation, median, proportion of participants at each score level). No formal statistical tests will be conducted. Interpretation of results will be rule-based.

Rules for data interpretation. Device use is feasible if at baseline, 1-week, or 1-month 50% or more of total number of participants score 3 or greater out of 5.

Feasibility Questionnaire

Data analysis. Participants' scores will be the sum of items 1 to 11 and will range from 0 to 11. Analysis will consist of summary descriptive statistics (mean, standard deviation, median, proportion of participants at each score level). No formal statistical tests will be conducted. Interpretation of results will be rule-based.

Rules for data interpretation. Device use is feasible if at 1-week or 1-month 50% or more of total number of participants score 6 or greater out of 11.

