9.4.9 Exploratory Analyses

We will compare the feasibility and efficacy of the OrCam use in the CLN3 versus non-CLN3 groups. We will evaluate data collected on unanticipated use (uses identified by participants and not an advertised feature) of OrCam MyEye 2 and correlation of use feasibility and ability to measures of disease status (e.g., disease severity, neuropsychologic ability, etc.) using summary statistics. Exploratory analyses of clinical and biochemical markers may be done under protocol 18-CH-0002.

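### The planned CLN3 versus non-CLN3 comparison has no between-group estimate or interval, so cohort pass/fail verdicts could stand in for one

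*Combined protocol and SAP*

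**What the plan says.** The synopsis (1.1) plans 30 children: "20 with CLN3-related conditions, 10 without CLN3". The first exploratory objective in Section 3 is "To compare the feasibility and efficacy of using the device between the CLN3 and non-CLN3 groups", and Section 9.4.9 repeats the commitment: "We will compare the feasibility and efficacy of the OrCam use in the CLN3 versus non-CLN3 groups".

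Section 9.4.7 gives the whole of the sub-group method: "Analyses of the sub-groups will be as described in Sections 9.4.2 and 9.4.3". For the feasibility measures, Section 9.4.2 lists the mean, standard deviation, median and distribution of scores, then states: "No formal statistical tests will be conducted. Interpretation of results will be rule-based". Section 9.4.3 takes the same position for the Function Test and the Ability Questionnaire. The feasibility rules are:

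- Feasibility Test: "Device use is feasible if at baseline, 1-week, or 1-month 50% or more of total number of participants score 3 or greater out of 5".
- The Feasibility Questionnaire: "Device use is feasible if at 1-week or 1-month 50% or more of total number of participants score 6 or greater out of 11".

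The Function Test rule in 9.4.3 calls the device efficacious if at least 25% of participants improve by at least 30%, at 1 week or at 1 month. Section 9.4.1 covers before/after comparisons and correlations. It does not cover two independent groups.

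**The concern.** Read together, these sections give each cohort a set of summaries and a verdict, and nothing that measures the gap between cohorts. A pass in one cohort and a fail in the other is not evidence that they differ: each verdict is a noisy dichotomy, and two of them can disagree by chance alone. A report following this text could conclude that the device is feasible in low vision but not in CLN3 when diagnosis makes no difference.

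Section 9.2 says the pilot data will inform the power calculations of a later trial. A chance cohort verdict could carry over into its design.

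**Working it through.** **The plan's own figure.** There is none for this comparison. The only power figures (Section 9.4.3, Simulations 1-6) concern a paired before/after t-test in 10 participants and do not bear on a between-group question.

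**Inputs.** Cohort sizes are 20 and 10 (1.1). The 50% rule then needs 10/20 or 5/10. The 25% rule needs 5/20 or 3/10, because 25% of 10 is 2.5 and Section 9.4.3 itself rounds this up to 3. The rules refer to the total number of participants. For a sub-group I use the cohort's own size, since 10 children cannot supply half of 30. The true rate is not in the documents, so I assume a common rate p and vary it.

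**Formula, one time point.** Let A = P(X ≥ r₂₀ | 20, p) and B = P(X ≥ r₁₀ | 10, p), both exact binomial. The probability of opposite verdicts is A(1−B) + B(1−A).

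| Rule | p | A (CLN3 passes) | B (non-CLN3 passes) | Opposite verdicts |
|---|---|---|---|---|
| 50% | 0.40 | 0.245 | 0.367 | 43% |
| 50% | 0.464 (peak) | 0.459 | 0.532 | 50.3% |
| 50% | 0.50 | 0.588 | 0.623 | 48% |
| 50% | 0.60 | 0.872 | 0.834 | 25% |
| 50% | 0.70 | 0.983 | 0.953 | 6% |
| 25% | 0.15 | 0.170 | 0.180 | 29% |
| 25% | 0.244 (peak) | 0.561 | 0.456 | 50.5% |
| 25% | 0.30 | 0.762 | 0.617 | 44% |
| 25% | 0.40 | 0.949 | 0.833 | 20% |
| 25% | 0.50 | 0.994 | 0.945 | 6% |

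On the 25% rule at a true 25%, CLN3 passes 58.5% of the time and non-CLN3 47.4%. This is partly because the same rule asks for 25% of one group (5/20) and 30% of the other (3/10).

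**Any visit counts.** The written rules pass a group at any of three visits (Feasibility Test) or two (Feasibility Questionnaire, Function Test). With k independent visits and the same p at each, A becomes 1−(1−A)^k, and B likewise. For the questionnaire at p = 0.40, A = 1−0.755² = 0.43 and B = 1−0.633² = 0.60, so opposite verdicts occur 0.43×0.40 + 0.60×0.57 = 51% of the time. I also simulated a between-visit correlation of 0.7 on a latent normal scale. Both correlations are assumptions.

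| Rule as written | p | Opposite verdicts, correlation 0 to 0.7 |
|---|---|---|
| Feasibility Test, 3 visits | 0.40 | 47% to 51% |
| | 0.50 | 12% to 28% |
| | 0.60 | 1% to 6% |
| Feasibility Questionnaire, 2 visits | 0.40 | about 51% |
| | 0.50 | 26% to 36% |
| | 0.60 | 4% to 11% |
| Function Test, 2 visits | 0.20 | 49% to 50% |
| | 0.25 | 36% to 43% |
| | 0.30 | 19% to 29% |

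The peak stays at about 50 to 53% and moves to a lower true rate: roughly 35 to 40% for the feasibility rules and roughly 20% for the Function Test.

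**Group size.** Evaluable groups of 18/9, 16/8 and 15/7 also peak at about 50% at a single time point. When A = B = 0.5, the formula gives 0.5 whatever the group sizes.

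**What an interval would show.** Take 9/20 (fail) against 5/10 (pass) at one time point. The Wilson limits are 0.258 to 0.658 and 0.237 to 0.763. Newcombe: −0.05 − √(0.192² + 0.263²) = −0.376, and −0.05 + √(0.208² + 0.263²) = +0.286. The verdicts are opposite, yet the data are compatible with a large difference in either direction.

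**The case against.** The strongest reply is that the plan never says verdicts will be compared. Section 9.4.7 also brings in means, medians and score distributions, and 9.4.9 says only that the groups will be compared. That stands. A reader might infer a stated comparison of verdicts, but the documents support only a gap that leaves room for one.

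Second, Section 3 lists for this objective the Function Test Feasibility Scores and the Feasibility, Ability and Applicability questionnaires. It does not list the Feasibility Test or the Function Test Efficacy Scores, and Section 9 gives no rule for the Function Test Feasibility Scores or the Applicability Questionnaire. That also stands in part. The 50% rule reaches the comparison directly through the Feasibility Questionnaire. The 25% rule reaches it through 9.4.7 and the word efficacy in 9.4.9. I did not size the Ability Questionnaire rule, because its 25% increase is not said to be relative or absolute.

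Third, a reader might blame the 20/10 split, or take the single-visit 48% at a true 50% as the plan's rate. Neither holds. The peak comes from comparing two verdicts at all, and with a pass at any visit the questionnaire figure at 50% is 26 to 36%.

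Fourth, it is tempting to read "For age- and visual severity level-appropriate comparisons, individuals with low vision but not CLN3 will also be children" (5.3.2) as a promise of an adjusted comparison. In context it explains why the controls are children. Age and acuity may differ between cohorts, but the documents give no figures from which to size that effect.

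Finally, this is a pilot, and Section 9.4.3 itself leaves open whether 10 participants can support conclusions about sample characteristics. That limits the stakes but does not supply a method.

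**Conclusion.** The concern holds in a limited form. The plan commits to a between-group comparison and specifies no estimate of it, and its only interpretive device at cohort level is a verdict. If verdicts are used, equal groups disagree about half the time near the effective cut-off and rarely far from it. No true rate is known in advance (9.2), so rates near the cut-off cannot be excluded.

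The figures assume a common true rate, independent children, each cohort's own size as denominator and, for the any-visit results, an equal rate at each visit with correlation between 0 and 0.7. Section 4.1 bases the primary and secondary objectives on all 30 participants, so nothing here touches those conclusions.

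**What to change.** In 9.4.7 and 9.4.9, state that the pass/fail rules are not used by cohort to infer a difference. At each time point report, labelled descriptive:

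- the CLN3 minus non-CLN3 difference in each proportion, with a Newcombe 95% interval and the number evaluable in each cohort;
- the difference in each mean score, with a 95% CI;
- baseline age and acuity by cohort beside these.

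An age- and acuity-adjusted score difference can be an optional sensitivity analysis. It would need acuity categories defined within the below-20/200 range, and it will be imprecise with 30 children.

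The cost is a few lines of text and code, with no new data or visits. The drawback is width. The approximate half-width 1.96√[p(1−p)(1/20 + 1/10)] is 38 points at p = 0.50 and 33 points at p = 0.25. Showing that imprecision is the purpose of the change, because a pair of verdicts hides it.

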9.4.8 Tabulation of individual Participant Data

Not applicable.

9.4.9 Exploratory Analyses

We will compare the feasibility and efficacy of the OrCam use in the CLN3 versus non-CLN3 groups. We will evaluate data collected on unanticipated use (uses identified by participants and not an advertised feature) of OrCam MyEye 2 and correlation of use feasibility and ability to measures of disease status (e.g., disease severity, neuropsychologic ability, etc.) using summary statistics. Exploratory analyses of clinical and biochemical markers may be done under protocol 18-CH-0002.

10 REGULATORY AND OPERATIONAL CONSIDERATIONS

10.1 INFORMED CONSENT PROCESS

10.1.1 Consent/Assent Procedures and Documentation

The informed consent document will be provided as a physical or electronic document to the participant or consent designee as applicable for review prior to consenting. A designated study investigator will carefully explain in terms suited to their comprehension the purposes, procedures, and tests involved in this study, and the associated risks, discomfort, and benefits. To minimize potential coercion, as much time as is needed to review the document will be given, including an opportunity to discuss it with friends, family members and/or other advisors, and to ask questions of any designated study investigator prior to signing. A signed informed consent document will be obtained prior to any research activities taking place.

The initial consent process as well as re-consent, when required, may take place in person or remotely (e.g., via telephone or other NIH approved remote platforms used in compliance with policy, including HRPP Policy 303) per discretion of the designated study investigator and with the agreement of the participant/consent designee(s). Whether in person or remotely, the privacy of the subject will be maintained. Consenting investigators (and participant/consent designee, when in person) will be located in a private area (e.g., clinic consult room). When consent is conducted remotely, the participant/consent designee will be informed of the private nature of the discussion and will be encouraged to relocate to a more private setting if needed. If the consent process is occurring remotely, participants and investigators will view individual copies of the approved consent document either on paper or on screens at their respective locations; the same screen or paper document may be used when both the investigator and the participant are co-located but this is not required. When required, the witness signature will be obtained similarly as Template version date 10.27.2020

Abbreviated Title: Pediatric Optic-to-Audio Device Study

Version Date: March 8, 2022

described for the investigator and participant below.

Consent will be documented with required signatures on the physical document (which includes the printout of an electronic document sent to the participant) or on the electronic document and made part of the participant's NIH record. The process for documenting signatures on an electronic document is described below.

When a hand signature on an electronic document is used for the documentation of consent, this study will use the following electronic platforms to obtain the required signatures:

- Adobe Acrobat platform (which is 21 CFR Part 11 compliant); or
- iMedConsent platform (which is 21 CFR Part 11 compliant)

Both the investigator and the participant will sign the electronic document using a finger, stylus, or mouse. Electronic signatures (i.e., the "signature" is digitally generated) will not be used.

We will obtain written informed consent from the parents /guardian(s) who accompany the child to the NIH Clinical Center (CC). If the parents are divorced and share custody, we will obtain consent from both parents. If the second parent is unable to attend the visit, the second parent will be consented via telephone or other NIH approved remote platforms as described above. An individual who is not associated with the protocol must witness the signature of the absent parent/guardian on the consent form. According to 45 CFR

46.408 when one parent is deceased, unknown, incompetent, or not reasonably available, or when only one parent has legal responsibility for the care and custody of the child, the permission of one parent suffices. Where deemed appropriate by the clinician and the child's parent(s) or guardian, the child will also be included in all discussions about the trial and age-appropriate language will be used to describe the procedures and tests involved in this study, along with the risks, discomforts, and benefits of participation. Verbal assent will be obtained as appropriate for children ages 6-10. Children under the age of 18, but who are age > 10 years will be asked to sign an age-appropriate assent form. Children under the age of 6 years are not eligible for enrolment. The consent/assent process will be documented in the child's medical record, including the assessment of the child's ability to provide assent (verbal versus written) as applicable. If applicable, children will be contacted after they have reached the age of 18 to determine whether they wish to continue on the trial and informed consent will be obtained from them at that time.

10.1.2 Consent for minors when they reach the age of majority

When a pediatric subject reaches age 18, continued participation (including ongoing interactions with the subject or continued analysis of identifiable data) will require that consent be obtained from the now adult with the standard protocol consent document to ensure legally effective informed consent has been obtained.

If reconsent is not feasible, we request waiver of informed consent to continue to use data and/or specimens for those individuals who become lost to follow up or who have been taken off study prior to reaching the age of majority.

Requirements for Waiver of Consent consistent with 45 CFR 46.116 (d):

- (1) The research involves no more than minimal risk to the subjects.
 - a. Analysis of samples and data from this study involves no additional risks to subjects.
- (2) The research could not practicably be carried out without the waiver or alteration.

Abbreviated Title: Pediatric Optic-to-Audio Device Study

Version Date: March 8, 2022

- a. Considering the length of time between the minor's last contact with the research team and their age of majority, it will likely be very difficult to locate them again. A significant reduction in the number of samples analyzed is likely to impact the quality of the research.
- (3) As the research involves using identifiable private information or identifiable biospecimens, the research could not practicably be carried out without using such information or biospecimens in an identifiable format.
 - a. Though the purpose of future studies cannot yet be known, they often involve the correlation of clinical outcomes and clinical interventions with laboratory studies. Such information would be unavailable if access to medical record numbers was unavailable.
- (4) The waiver or alteration will not adversely affect the rights and welfare of the subjects.
 - a. Retention of these samples or data does not affect the welfare of subjects.
- (5) Whenever appropriate, the subjects will be provided with additional pertinent information after participation.

10.1.3 We only request a waiver of consent for those subjects who have been lost to follow-up or who have been taken off study prior to reaching the age of majority. Considerations for Consent of NIH staff, or family members of study team members

Consent for NIH staff or family members of study team members will be obtained as detailed above with following additional protections:

Consent will be obtained by an individual independent of the staff member's team whenever possible. Otherwise, the consent procedure will be independently monitored by the CC Department of Bioethics Consultation Service to minimize the risk of undue pressure on the staff member.

10.2 STUDY DISCONTINUATION AND CLOSURE

This study may be temporarily suspended or prematurely terminated if there is sufficient reasonable cause. Written notification, documenting the reason for study suspension or termination, will be provided by the suspending, or terminating party to study participants, investigator, and regulatory authorities. If the study is prematurely terminated or suspended, the Principal Investigator (PI) will promptly inform study participants and the Institutional Review Board (IRB) and will provide the reason(s) for the termination or suspension. Study participants will be contacted, as applicable, and be informed of changes to study visit schedule.

Circumstances that may warrant termination or suspension include, but are not limited to:

- Determination of unexpected, significant, or unacceptable risk to participants
- Demonstration of efficacy that would warrant stopping
- Insufficient compliance to protocol requirements
- Data that are not sufficiently complete and/or evaluable
- Determination that the primary endpoint has been met
- Determination of futility

Study may resume once concerns about safety, protocol compliance, and data quality are addressed, and satisfy the IRB.

Abbreviated Title: Pediatric Optic-to-Audio Device Study

Version Date: March 8, 2022

